3.8.3. Selection of Data in the Event of Multiple Records in a Window

Depending on the statistical analysis method, single values are required for each analysis window. For example, change from baseline by visit usually requires a single value, whereas a time-to-event analysis would not require 1 value per analysis window. When a single value is needed, the following rule(s) will be used.

For baseline of the double-blind and open-label phases, the last available record on or prior to the first dose of blinded and open-label study drug will be selected, respectively. If there are multiple records with the same time or no time recorded on the same day for numeric observations, the average will be computed for that day, except for HBV DNA [IU/mL] and quantitative HBsAg [IU/mL], where the geometric mean will be computed instead. If there are multiple records with the same time or no time recorded on the same day for categorical observations, the most conservative value will be taken, eg, negative will be selected over positive for HBeAg, and positive will be selected over negative for HBeAb and HBsAb.

The following specified rules will be used for postbaseline visits:

- **ALT:** The largest value will be included in the analysis when 2 or more ALT values occur within the same visit window.
- **BMD:** The latest record in the window will be selected.

- **HBV DNA and quantitative HBsAg:** The record closest to the nominal day for that visit will be selected. If there are 2 records equidistant from the nominal day, the latest will be selected. If there is more than 1 record on the selected day, the geometric mean will be taken.
- **Serology:** For HBeAg, HBeAb, and HBsAb, the record closest to the nominal day for that visit will be selected. If there are 2 records equidistant from the nominal day, the latest will be selected. If there is more than 1 record on the selected day, the most conservative value will be taken, ie, positive will be selected over negative for HBeAg, and negative will be selected over positive for HBeAb and HBsAb.

For all other laboratory parameters:

- If multiple valid non-missing numeric observations exist in a window, then records will be chosen as follows:
 - The record closest to the nominal day for that visit will be selected. If there are 2 records equidistant from the nominal day, the latest will be selected. If there is more than 1 record on the selected day, the average will be taken.
- If multiple valid non-missing categorical observations exist in a window, then records will be chosen as follows:
 - The most conservative value within the window will be selected. In the event that 2 values within a window are of equal abnormality, the value collected nearest to the nominal date will be used.

4. SUBJECT DISPOSITION

4.1. Subject Enrollment

The number and percentage of subjects enrolled in each region, country, and by each investigator will be summarized by treatment group and overall using the Randomized Analysis Set. The number and percentage of subjects enrolled in each randomization stratum will be summarized based on IWRS data. A listing of subjects with discrepancies in the value used for stratification assignment between the IWRS and the clinical database at the time of data finalization will be provided.

The randomization schedule used for the study will be provided as an appendix to the CSR.

4.2. Disposition of Subjects

The summary of subject disposition will be provided by treatment group and overall. This summary will include the number of subjects screened, subjects not randomized, screen failure subjects who were not randomized, subjects who met all eligibility criteria and were not randomized with reasons for subjects not randomized, subjects in the Randomized Analysis Set, subjects randomized and not treated, and subjects in the Safety Analysis Set.

In addition, the number and percentage of the subjects in the following categories will be summarized using the Safety Analysis Set:

Double-Blind Phase

- Completed double-blind study drug
 - Completed double-blind study drug at Week 72
 - Completed double-blind study drug at Week 48
- Premature discontinuation of double-blind study drug (with summary of reasons for discontinuation of double-blind study drug)

Open-Label Phase

- Entered open-label phase at Week 72
- Entered open-label phase at Week 48
- Continuing open-label study drug
 - Entered open-label extension
- Completed open-label study drug
- Premature discontinuation of open-label study drug (with summary of reasons for discontinuation of open-label study drug)

TFFU Phase

- Entered the 24-week treatment-free follow-up period
- Completed the 24-week treatment-free follow-up period
- Entered the 24-week treatment-free follow-up period, but discontinued due to starting another HBV therapy

Study Completion

- Continuing study
- Completed protocol-planned duration of study
- Premature discontinuation of study (with summary of reasons for premature discontinuation of study)

No inferential statistics will be generated. A flowchart will be provided to depict the disposition. Also, the following by-subject listings will be provided by subject identification (ID) number in ascending order to support the above summary tables:

- Subject disposition including reasons for premature study drug or study discontinuation
- Screen failed subjects with reasons for screen failure

4.3. Extent of Blinded Study Drug Exposure and Adherence

Extent of exposure to study drug will be examined by assessing the total duration of exposure to blinded study drug and the level of adherence to the blinded study drug specified in the protocol.

4.3.1. Duration of Exposure to Blinded Study Drug

Duration of exposure to blinded study drug will be defined as (last dose date of blinded study drug – first dose date of blinded study drug + 1 day), regardless of temporary interruptions in study drug administration, and will be expressed in weeks (recorded to 1 decimal place, eg, 4.5 weeks). Please refer to Section 3.8.1 for details on the definition of the last dose date of blinded study drug.

Duration of exposure to blinded study drug will be summarized using descriptive statistics (sample size, mean, SD, median, Q1, Q3, minimum, and maximum) and as the number and percentage of subjects exposed for specified periods, eg, ≥ 4 weeks (28 days), ≥ 8 weeks (56 days), ≥ 16 weeks, ≥ 24 weeks, ≥ 32 weeks, ≥ 40 weeks, ≥ 48 weeks, ≥ 56 weeks, ≥ 64 weeks, and up to ≥ 72 weeks.

Summaries will be provided by treatment group for subjects in the Safety Analysis Set. No inferential statistics will be provided.

4.3.2. Adherence with Blinded Study Drug Regimen

The amount of blinded study drug dispensed and returned was captured on the Study Drug Accountability form. Adherence will be summarized for blinded study drug during both the double-blind phase (eg. some subjects took blinded study drug up to Week 72, while some subjects only took blinded study drug up to Week 48) and up to Week 48 only. To determine adherence up to Week 48, only records in the Study Drug Administration eCRF prior to the Week 48 Protocol Visit will be used.

Adherence (%) with blinded study drug will be calculated as follows:

$$\text{Adherence (\%)} = 100 \times \frac{\text{Amount of Blinded Study Drug Taken [1]}}{\text{Amount of Blinded Study Drug Expected To Be Prescribed [2]}}$$

If calculated adherence is greater than 100%, then adherence will be set to 100%.

A dispensation period will be defined as a single entry into the Study Drug Administration eCRF. If any blinded study drug bottle is not returned or unknown (missing return date or ongoing) or the amount of blinded study drug dispensed is missing, then all of the records for the corresponding dispensation period will be excluded from both denominator and numerator in the calculation. For a dispensation period where the amount of blinded study drug returned is missing (but a date of return is available), it is assumed the amount of blinded study drug returned is zero.

[1] Amount of blinded study drug taken is determined by first converting the amount of blinded study drug from the powder or tablet formulation into mg of TDF or matching placebo, then subtracting the total amount of blinded study drug returned from the total amount of blinded study drug dispensed.

Specifically, if blinded study drug is administered as the powder formulation, then the amount of blinded study drug is multiplied by 40 (ie, 40 mg of blinded study drug per 1 gram of powder). If blinded study drug was administered as the tablet formulation, then the amount of blinded study drug is multiplied by 150 mg, 200 mg, 250 mg or 300 mg as indicated by the dose unit of blinded study drug dispensed. After conversion, the total amount of blinded study drug taken is calculated as the total amount of blinded study drug dispensed (mg) across all dispensation periods minus the total amount of blinded study drug returned (mg) across all dispensation periods.

[2] Amount of blinded study drug prescribed can be calculated using the following three steps: (1) collapse, (2) impute, and then (3) sum.

1. The first step is to collapse the dispensation periods by first sorting them by dispensation date in increasing order, and then for all dispensation periods with the same dispensation date, collapse into one dispensation period by setting the return date for the collapsed dispensation period to be the maximum of the corresponding return dates. If multiple blinded study drug formulations (ie, powder or tablet and dosage) are dispensed on the same dispensation date,

then the blinded study drug formulation selected to represent the collapsed dispensation period will be the blinded study drug formulation with the largest difference between the amount of blinded study drug prescribed and blinded study drug returned (in terms of mg of blinded study drug).

2. The next step is to impute the return dispensation date for the collapsed dispensation periods to be the **day prior** to the minimum of the return date + 1 day, date of first dose of open-label study drug, date of last dose of blinded study drug formulation + 1 day, and dose dispensation date for the next collapsed dispensation period. The date of first dose of open-label study drug and date of last dose of blinded study drug formulation can be found on the Study Drug Administration eCRF. If the subject did not take open-label study drug, then date of first dose of open-label study drug will be excluded from the calculation.
3. The last step is to sum across the amount of blinded study drug expected to be prescribed for each collapsed and imputed dispensation period. The amount of blinded study drug expected to be prescribed for a given dispensation period can be calculated by first converting the prescribed study drug formulation to mg of TDF or placebo, and then multiplying by the duration of treatment, defined as the imputed return date – the dispensation date + 1 day.

Specifically, for subjects who took blinded study drug as an oral powder on the date of dispensation, based on the weight on the date of dispensation (use last available weight if weight on that day is not available from the vital signs dataset), multiply the duration of treatment during by one of the following expected daily doses of blinded study drug:

80 mg for 10 to <12 kg (22 to <26 lbs)
100 mg for 12 to <14 kg (26 to <31 lbs)
120 mg for 14 to <17 kg (31 to <37 lbs)
140 mg for 17 to <19 kg (37 to <42 lbs)
160 mg for 19 to <22 kg (42 to <49 lbs)
180 mg for 22 to <24 kg (49 to <53 lbs)
200 mg for 24 to <27 kg (53 to <60 lbs)
220 mg for 27 to <29 kg (60 to <64 lbs)
240 mg for 29 to <32 kg (64 to <71 lbs)
260 mg for 32 to <34 kg (71 to <75 lbs)
280 mg for 34 to <35 kg (75 to <77 lbs)
or 300 mg for ≥ 35 kg (≥ 77 lbs).

For subjects who took blinded study drug as tablets on the date of dispensation, multiply the duration of treatment by 150 mg, 200 mg, 250 mg, or 300 mg for subjects weighing <22 kg (37 to <49 lbs), 22 to <28 kg (49 to <62 lbs), 28 to <35 kg (62 to <77 lbs), and ≥ 35 kg (≥ 77 lbs), respectively.

After calculating the amount of blinded study drug expected to be prescribed for each collapsed and imputed dispensation period, then the amount of blinded study drug expected to be prescribed in [2] is calculated by summing across all collapsed and imputed dispensation periods.

Adherence will be calculated for each subject for the entire double-blind phase and up to Week 48. A descriptive and categorical [$< 80\%$, $80 - < 90\%$, $90 - < 95\%$, and $\geq 95\%$] summary will be provided for subjects in the Safety Analysis Set by treatment group. No inferential statistics will be provided.

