5.2.2. Packaging and Labeling

Thirty (30) tenofovir DF tablets or matching placebo tablets are packaged in white, high-density polyethylene (HDPE) bottles with one gram of desiccant and fiber packing present in each bottle. Each bottle is enclosed with a white, continuous thread, child-resistant polypropylene screw cap with an induction-sealed, aluminium-faced liner.

Sixty (60) grams of tenofovir DF oral powder formulation or matching placebo powder formulation are packaged in white, high density polyethylene (HDPE) bottles. Each bottle is capped with a white, continuous thread, child-resistant polypropylene screw cap with an induction-sealed, aluminum-faced liner. One or more polypropylene dosing scoops will be provided with each bottle.

Study drug to be distributed to centers in the US and other participating countries shall be labeled to meet applicable requirements of the United States Food and Drug Administration (FDA), EU Guideline to Good Manufacturing Practice - Annex 13 (Investigational Medicinal Products), and/or other local regulations.

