3.1.4. Per Protocol Analysis Set

The Per Protocol (PP) Analysis Set will include all subjects who (1) were randomized into the study, (2) had received at least 1 dose of study drug, and (3) had not been excluded based on criteria below. Subjects will be analyzed according to the treatment they actually received during the double-blind phase. The PP analysis set is the secondary analysis set for the efficacy analysis.

Subjects meeting any of the following criteria will be excluded from the Week 48 PP Analysis Set:

- Subjects who do not have on-treatment HBV DNA in the Week 48 analysis window, except for subjects who discontinue study drug due to lack of efficacy. (Note: lack of efficacy is defined as having the check-box for “Efficacy Failure” marked as the reason for premature study drug discontinuation on the study drug completion eCRF page). The details are summarized in [Table 3-1](#).

Table 3-1. Subjects Excluded from Per Protocol Analysis Set Due to Premature Discontinuation and/or Missing HBV DNA Assessment in Week 48 Analysis Window

Discontinuation from Study Drug Prior to or on the Upper Bound of Week 48 Analysis Window		HBV DNA Data on Randomized Treatment Available in Week 48 Analysis Window	
		Yes	No
Yes	Due to Lack of Efficacy	+	+
	Due to Other Reasons	+	-
No		+	-

+ = Inclusion of Subjects in Per Protocol Analysis Set; - = Exclusion of Subjects in Per Protocol Analysis Set

- Subjects who meet the exclusion criterion for receiving ongoing therapy with any of the prohibited medications listed in the clinical study protocol (Section 4.3).
- Subjects with less than 80% adherence rate for study drug up to the Week 48 visit.

A listing of subjects in the FAS, but were excluded from the PP Analysis Set, will be provided with the reason for exclusion specified.

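### SAP 4.3.2 can drop an unreturned bottle from the adherence numerator but leave its days in the denominator, because exclusion works per eCRF entry and same-date entries are merged only for the denominator

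*SAP*

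**What the plan says.** SAP 4.3.2 defines adherence as drug taken divided by drug expected, both in mg.

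- **Unit.** "A dispensation period will be defined as a single entry into the Study Drug Administration eCRF". The amounts come from a differently named form: "The amount of blinded study drug dispensed and returned was captured on the Study Drug Accountability form".
- **Exclusion.** If any bottle is unreturned or its status is unknown, or the dispensed amount is missing, "then all of the records for the corresponding dispensation period will be excluded from both denominator and numerator in the calculation".
- **Numerator.** Drug taken is found by "subtracting the total amount of blinded study drug returned from the total amount of blinded study drug dispensed", across dispensation periods. No merging is mentioned here.
- **Denominator.** Step 1 says that "for all dispensation periods with the same dispensation date, collapse into one dispensation period". Steps 2 and 3 then multiply the expected daily dose by the calendar days of the merged interval.
- **Missing return count.** Where a return date exists but no amount, "it is assumed the amount of blinded study drug returned is zero".

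The result decides membership of an analysis set. SAP 3.1.4 removes from the Per Protocol set "Subjects with less than 80% adherence rate for study drug up to the Week 48 visit". SAP 6.1.4 repeats the primary analysis on that set.

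**The concern.** The exclusion rule is meant to be neutral: a period whose intake is unknown should count neither for nor against the child. That works only if the same unit leaves both sums. Here the excluded unit is the entry, while the denominator is built from all entries that share a date. If one same-date entry is dropped and another survives, the survivor can still carry the full interval into the denominator, and the child is scored as if the dropped drug had not been taken.

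Several bottles per visit are unavoidable. Protocol 5.2.2 gives 30 tablets or 60 g of powder per bottle, and visits from Week 8 to Week 48 are 56 days apart. Step 1 itself expects several entries on one date.

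At stake are who is in the Per Protocol set, among 89 treated children (SAP 1.3), and the adherence summary by arm. The missing-count rule pushes scores the other way and can keep a poorly adherent child in the set.

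**Working it through.** The SAP gives no worked adherence figure to reproduce, so the formula was applied to model children.

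**Inputs**
- Blinded dispensing at Weeks 0, 4, 8, 16, 24, 32 and 40, with Week 48 as the end (Protocol 6.1.2, 6.2.1, 6.2.2): two 28-day and five 56-day intervals, 2×28 + 5×56 = 336 days.
- 30 tablets or 60 g per bottle (Protocol 5.2.2); 40 mg per gram (Protocol 5.2.1.2).
- Cut-off 80% (SAP 3.1.4).

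**Assumptions**
- One eCRF entry per bottle, with exclusion before the same-date merge.
- Just enough bottles to cover each interval, used one after another and due back at the next visit.
- Every dose taken, except where stated.

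**Nothing missing.** 336/336 = 100%. The formula behaves correctly when all bottles come back.

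**One 56-day interval, tablets.** Two bottles; 30 doses come from the first and 26 from the second. If the emptied bottle is not returned, its 30 doses leave the numerator. The second entry still spans 56 days: 26/56 = 46.4%.

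**Full 48 weeks, tablets, n emptied bottles missing from separate intervals:** (336 − 30n)/336
- n = 1: 306/336 = 91.1%
- n = 2: 276/336 = 82.1%
- n = 3: 246/336 = 73.2%

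If the part-used bottle is the one lost (26 doses each), the scores are 310/336 = 92.3%, 284/336 = 84.5% and 258/336 = 76.8%. Either way, three are needed.

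**Powder at 160 mg/day.** 160/40 = 4 g/day, so a bottle lasts 60/4 = 15 days. Four missing: (336 − 60)/336 = 82.1%. Five missing: (336 − 75)/336 = 77.7%. Across the dosing bands, the number needed runs from three (2.0 to 2.5 scoops) to nine (7.5 scoops).

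**Shorter exposure, tablets.** One missing bottle in a course ending at Day 112 gives 82/112 = 73.2%; two in a course ending at Day 280 give 220/280 = 78.6%. Without Week 48 HBV DNA, such children can be in the Per Protocol set only if they stopped for lack of efficacy (SAP Table 3-1).

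**Where the mismatch vanishes**
- A 28-day tablet interval has one bottle, so both sums drop together.
- If all bottles of an interval are missing, both sums drop: three whole intervals lost give 168/169 = 99.4%.
- If one missing bottle removes the whole same-date period, a fully adherent child scores 98.2% to 99.6% in every scenario run. The small shortfall is one extra day: the interval before an excluded one ends on its return date and not on the day before.

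**Missing return counts.** A child who truly takes 75% takes 252 of 336 doses. In a 56-day interval, 60 tablets are dispensed, 42 taken and 18 returned. With the returned amount set to zero, the 18 count as taken.
- One such interval: (252 + 18)/336 = 80.4%
- Two such intervals: (252 + 36)/336 = 85.7%

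This result does not depend on what an entry is.

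**The case against.** The strongest reply is that the SAP says in terms that the period leaves both sums, so the mismatch exists only under a reading the text does not compel. The rule speaks of any bottle and of all the records for a period, which suits an entry holding a visit's whole supply at least as well as a one-bottle entry. Same-date entries do not prove one entry per bottle, since step 1 also provides for different formulations dispensed together. The order of exclusion and merging is not stated either.

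Much of this stands. The eCRF layout cannot be settled from the documents, and if an entry is a whole visit's supply, there is no mismatch between its bottles. It does not remove the point. The exclusion is attached to the single entry, the merge appears only inside the denominator, and step 1 expects same-date entries. If different formulations are separate entries, dropping one still leaves the other's interval in the denominator.

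It is also fair that Protocol 5.5 requires all used and unused drug to be returned, that analysis sets are fixed before unblinding (SAP 3.1), and that exclusions from the Per Protocol set are listed with reasons (SAP 3.1.4). An odd exclusion could therefore be noticed. Nothing in the documents suggests that the pattern is common or differs by arm.

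The missing-count rule is an explicit, prespecified convention. The arithmetic against it holds, but replacing it is more a matter of judgement.

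**Conclusion.** The point holds as a gap between the SAP's intent and its literal steps, with medium confidence. Where several entries share a dispensing date and one is dropped, the numerator can lose drug whose days stay in the denominator. With one entry per bottle, a fully adherent child on tablets needs three such bottles over 48 weeks to fall below 80% (five on powder at 160 mg/day).

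A reader might infer more, and the documents do not support it:
- That the formula plainly removes drug from the numerator only. The stated rule is the opposite; the failure depends on entry layout and order of steps.
- That one lost bottle excludes an adherent child. Over 48 weeks it leaves a tablet score of about 91%; only a short course crosses 80%.
- That the main result is at risk. The primary analysis uses the Full Analysis Set with missing = failure, which adherence does not enter.

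What is affected is Per Protocol membership and the descriptive adherence table by arm. The zero-return rule is a secondary issue that can raise 75% true intake to 80.4% or 85.7%.

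**What to change.** In SAP 4.3.2, collapse entries by dispensing date before anything else, and define the dispensation period as the collapsed period. If any bottle in it is unreturned or has a missing dispensed amount, exclude the whole collapsed period from numerator and denominator. This delivers the stated intent whether an entry is one bottle or a visit's supply.

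Preferably treat a missing returned amount in the same way. At the least, report that version as a check on who enters the Per Protocol set.

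The cost is about two sentences and a reordered programming step. The downside is that a few more intervals drop out of the adherence calculation.
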